All examinations and determinations of the individual measurement data are carried out by Dr. med. dent. [name], in his dental practice in Steina. The exercise instructions are supervised by [name] in the dental practice in Steina.

Baseline examination

For the baseline examination the patient's anamnesis is recorded and the dental status is ascertained.

A panoramic radiograph must be available prior to the treatment in order to assess dental health and ensure the success of the treatment and it must not be older than 6 months. Such an X-ray can be realized by the volunteer's general dentist or the specialized dental practice in Steina.

The functional examination is based on the standardized DC / TMD.

Also, the inclusion and exclusion criteria for the planned form of therapy are checked. The assessment of the degrees of strength according to Janda during the lateral movement of the mandible requires a pain-free and coordinated sequence of movements. Subjects who experience unilateral or bilateral pain during this lower jaw movement cannot be included in the study.

The assessment of patients, who are assigned to the muscle training group and who are diagnosed with a pain-free, but uncoordinated movement pattern, is based on the

Groot Landeweer coordination scale (I-III). The subjects who only achieve Grade II or III must first perform exercises to improve coordination during laterotrusion (exercises with a spatula). The development of the coordinative ability is reassessed through weekly checks. By achieving level I (according to Groot Landeweer), the strength level (according to Janda) for the lateral movement of the lower jaw can be determined. Instructions in muscle training can be given.

These examination procedures are part of the routine examination in the "TMD Competence Center Westlausitz" for patients with temporomandibular disorders.

Coordination according to Groot Landeweer [1]:

I Coordinated execution of the movement
II Execution of the movement only by using facial muscles and / or masticatory muscles
III Inability to perform the movement

Modified scale of the degrees of force according to Janda for laterotrusion [5]:

| 4- | Full movement against a slight resistance |
|----|--|
| 4 | Full movement against moderate resistance |
| 5- | Full movement against clear resistance |
| 5 | Full movement against strong resistance / maximum strength |

Randomization

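### For patients with an uncoordinated jaw movement, whether and when a starting Janda grade exists depends on the assigned arm, and the analysis plan has no rule for patients who cannot be graded

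*Combined protocol and SAP*

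**What the plan says.** The Secondary outcome variables section lists change in Janda force degree for lateral movement, on a modified four-level scale from 4- to 5. It names no visit as the starting point. Methods of data collection and the three control appointment sections collect the grade in all patients at 2, 4 and 6 months.

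The Baseline examination section sets the conditions:

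- Janda grading "requires a pain-free and coordinated sequence of movements".
- The bar to enrolment is narrower and concerns pain alone: "Subjects who experience unilateral or bilateral pain during this lower jaw movement cannot be included in the study".
- A further rule is introduced with "The assessment of patients, who are assigned to the muscle training group and who are diagnosed with a pain-free, but uncoordinated movement pattern". These patients are graded I to III on the Groot Landeweer coordination scale.
- Within that rule, "The subjects who only achieve Grade II or III must first perform exercises to improve coordination during laterotrusion (exercises with a spatula"). No maximum length is set for this phase; the only provision on its course is that "The development of the coordinative ability is reassessed through weekly checks", and on reaching level I "the strength level (according to Janda) for the lateral movement of the lower jaw can be determined".

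The section adds that these examinations are routine at the centre for patients with temporomandibular disorders. The Statistical analysis section plans a t-test and a Mann-Whitney U-test between groups. It does not mention patients without a grade.

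**The concern.** A change score compares randomised groups fairly only if the starting value is defined in the same way in both arms and does not depend on the assignment. Here the only described path from ungradable to graded belongs to one arm and begins after assignment.

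Two things could follow. If uncoordinated appliance patients have no starting grade and drop out of the change score, while uncoordinated exercise patients stay in with a later grade, the two analysed groups differ in make-up for a reason linked to the arm. If the later grade is used as the exercise arm's baseline, that baseline is a post-randomisation value in one arm only. The outcome concerned is the direct measure of the strengthening that the training is meant to produce.

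**Working it through.** The plan gives no figure on this point, so the check is mainly a comparison of its own statements.

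**1. Can an ungradable patient be enrolled?** Grading needs a movement that is both pain-free and coordinated. The enrolment bar in the Baseline examination section covers pain only. The Exclusion Criteria list age under 18, drug abuse, depression and polyarthritis. Nothing excludes an uncoordinated, pain-free patient from either arm.

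**2. Could such a patient be given a grade anyway?** The lowest Janda level, 4-, is defined as "Full movement against a slight resistance", and the three higher levels also describe a full movement. Coordination grade III is defined as "Inability to perform the movement", so a grade III patient has no value on the scale. A grade II patient moves only with the help of other muscles and so fails the coordination condition.

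**3. What happens next, by arm?**

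| Movement before assignment | Muscle training arm | Appliance arm |
|---|---|---|
| Coordinated, pain-free | Gradable at baseline | Gradable at baseline |
| Uncoordinated, pain-free | First possible grade after assignment and spatula training, on reaching level I; weekly checks, no stated limit | No route to a grade described |

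The rule in the lower middle cell stands under Baseline examination, ahead of the Randomization section. Because it covers patients already assigned to an arm, it can operate only once the arm is known.

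**4. Does the analysis plan close the gap?** No. It has no category, substitution or missing-data rule for an ungradable patient.

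**5. How many patients?** The documents do not give the share *s* at coordination grade II or III. As an assumption, take *s* from 10% to 50% in each arm. Patients per arm without a valid starting grade = 30 × *s*:

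- *s* = 10%: 30 × 0.10 = 3
- *s* = 25%: 30 × 0.25 = 7.5
- *s* = 50%: 30 × 0.50 = 15

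This counts patients without a starting grade; it is not an estimate of bias. A share near zero is also compatible with the documents.

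**The case against.** The strongest reply is that much of the harm rests on silence. The plan never says that uncoordinated appliance patients go ungraded or are dropped, and it calls the examination procedures routine for the centre's patients. The affected share is unknown and may be small. The outcome is one of three secondary variables, neither numbered hypothesis (pain, clicking) uses it as its outcome, and the sample size rests on pain alone. All of this is correct and limits the weight of the point. It does not remove it: routine coordination grading would show who is uncoordinated, but would still give an uncoordinated appliance patient no Janda grade.

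Some stronger readings are tempting but not supported:

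- A reader might infer that the exercise arm's change is planned to start from the grade taken after spatula training. No baseline visit is named for Janda. That grade is only the earliest one the plan's own condition permits. It follows coordination training, not muscle training.
- A reader might infer that strength gained in the coordination phase is lost from the exercise arm's change by a calculable number of steps. A gain from an ungradable state is undefined on this scale, and the Preliminary exercise section describes no resistance.
- A reader might infer that valid pre-randomisation Janda grades are lost for good. For these patients none can exist; only their gradability status could go unrecorded.
- A reader might infer a timing bias in the pain outcome, because the visits count from a start of therapy that is not defined for either arm. Natural readings exist (start of muscle training; integration of the appliance), and the documents give no interval from which to size an effect. This is missing detail only.

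**Conclusion.** The concern holds in a limited form. Followed as written, the plan lets uncoordinated patients into both arms, gives one arm a first Janda grade after assignment and coordination training, and describes no grade for the other. For these patients the availability and timing of the starting value depend on the arm, so the comparison of change in Janda grade may not be between comparable randomised groups.

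The size and direction of any bias cannot be computed. The count of 3–15 patients per arm rests entirely on the assumed share of 10–50%. Patients with a coordinated movement are not affected. Nor is the primary pain outcome: the Abstract fixes its baseline at the baseline examination, and pain rating does not depend on coordination. The point is worth correcting because the remedy is nearly free, not because a large distortion has been shown.

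**What to change.** At the baseline examination, before randomisation and in the same way for every patient, record the coordination grade and either the Janda grade or *not gradable*. Do not use a grade taken after coordination training as the baseline. The coordination phase itself is unchanged.

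Prespecify one of two analyses, applied alike to both arms:

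1. Compare change among patients gradable before randomisation, and report the others separately by arm. Selection then rests on a pre-randomisation feature, so the comparison stays randomised.
2. Keep all randomised patients by ranking *not gradable* below 4- in the planned Mann-Whitney test. The plan must then state how a move out of *not gradable* ranks as a change.

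The cost is protocol and analysis plan wording and one more baseline entry for appliance patients, possibly already routine. Option 1 also shrinks the Janda sample. With the 24 completers per arm on which the sample size is based, 24 × (1 − *s*) remain: 21.6 at 10%, 18 at 25% and 12 at 50%. For illustration, the power of a two-sided 5% t-test for an assumed difference of 1 SD (noncentral t with 2*n* − 2 degrees of freedom and noncentrality √(*n*/2)) is 92% at 24 per arm, 89% at 21.6, 83% at 18 and 65% at 12. The plan sets no Janda target difference and the scale has four levels, so these figures show only the order of the loss. Option 2 avoids that loss, but its result mixes regained coordination with strength.

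As a minor clarification, state what the start of therapy means in each arm and record that date for each patient.

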The stabilization appliance is incorporated by the dentist and the static and dynamic occlusion is checked. A tension-free fit of the appliance on the lower jaw is necessary. Additionally, equal contacts in the side teeth area and incisors guidance in the case of mandibular protrusion are checked visually and by using occlusion foil. During mandibular lateral movement only the canine guidance takes place and is also registered optically and by using occlusion foil. Interference contacts should be adjusted.

The patient is instructed to wear the stabilization appliance while sleeping. The wearing rhythm is described as intermittent. (three nights - wearing the appliance, one night – not wearing the appliance).

Control appointment for stabilization appliance group (1 week after integration)

The first inspection takes place one week after the integration. The surface contacts in the side teeth area as well as the incisor and canine guidance are checked again.

First control appointment (2 months after start of therapy)

Two months after starting the therapy, an examination is carried out with a renewed assessment of the functional status. The primary (pain when opening or closing movements of the mouth) and secondary (occurrence of the cracking phenomenon when opening or closing movements, Janda degrees of strength in lateral movement of the mandible, interincisal opening distance) target variables are recorded.

Second control appointment (4 months after start of therapy)

A second check is carried out 4 months after starting the therapy. The functional findings as well as the primary (pain when opening or closing the mouth movement) and secondary (occurrence of the cracking phenomenon when opening or closing the mouth movement, Janda strength levels for lateral movement of the mandible, interincisal opening distance) target variables are recorded.

Third control appointment (6 months after the start of therapy)

The last examination takes place 6 months after starting the therapy. The functional status as well as the primary (pain when opening or closing the mouth movement) and secondary (occurrence of the cracking phenomenon when opening or closing the mouth movement, Janda strength levels for lateral movement of the mandible, interincisal opening distance) target variables are recorded.

Patient Safety

Adverse events are recorded and the connection (certain, likely, unlikely) assessed. Serious or unexpected side effects are recorded on a separate form.

Risks of the treatment execution

There are no additional risks for the patients because the treatment methods of the study are based on routine clinical procedures.

During the muscle training, the volunteers may occasionally experience an increase in pain (similar to muscle soreness) and headache or dizziness may occur. However, these side effects should disappear after the first week and regular exercising. In addition, the untrained muscles can be overloaded in the beginning.

The basic risks of stabilization appliance therapy include allergic reactions to the material or incompatibilities in the oral cavity.

Temporary side effects can include: dry mouth or increased salivation, changes in occlusion, feeling of tension / pain in teeth, oral mucosa or tongue, gagging or bad taste. Loss of tooth crowns, fillings or other dentures can only occur in rare cases. When wearing an stabilization appliance over a longer period of time (months to years), permanent changes in the teeth can be established in some cases, such as tooth migration, opening of interdental spaces, loss of teeth with periodontitis or missing molar contacts.

In their entirety, risks and side-effects of these two treatment methods could be deem insignificant.

Termination Criteria

Adverse events can lead to premature termination of treatment. The following reasons could be possible:

- Intolerance or allergic reactions

- Pain on teeth, muscles or jaw joints that cannot be controlled
- Loosening of teeth
- Changes in tooth position or occlusion that cannot be tolerated
- Other physical or mental illnesses

A study termination must be documented in the patient's file by stating the corresponding reasons. A final examination of the volunteer is carried out. Patient safety must not be compromised. All safety and health examinations and treatments must be continued.

The justification for an early termination of the study is only necessary under the points given above.

Ethical and Regulatory Aspects

This study is carried out with special attention to the content of the following laws and guidelines:

- Declaration of Helsinki in its current version (Fortaleza, 2013)
- Medizinproduktegesetz MPG
- Medizinprodukte-Betreiberverordnung MPBetreibV
- Landesdatenschutzgesetz DSG M-V
- Datenschutzgrundverordnung EU-DSGVO

Independent ethics committee

The investigation will begin after consultation and approval by the responsible ethics committees and only if there are no ethical concerns. The head of this study ([name]. [name]) is responsible for submitting applications to the ethics committee of the University Medical Center Greifswald. The application to the ethics committee of the Free State of Saxony is submitted by [name] and Dr. med. dent. [name].

Patient information and consent

Participation in this study is only possible by a written consent. After Dr. med. dent. [name] or [name] have advised the patients, both orally and in writing, about the nature, meaning and scope of the study in an understandable manner, they will provide sufficient time to make a decision. By signing the consent, the volunteers declare their agreement with the recording of data required for the study. The patient can withdraw his consent at any time, without giving any reason and

The patient can withdraw his consent at any time, without giving any reason and experiencing any disadvantages.

The patient receives an original copy of the written patient information and consent in written or digital form. A second original is kept safe in the "CMD Competence Center Westlausitz".

Insurance

The study describes approved clinical forms of therapy that have successfully passed the conformity assessment procedure and are CE marked. No additional invasive or stressful examinations are performed on the patient. The course of this study is based on clinical routine. Therefore, the patient is not exposed to any study-related risks.

The treatment process and the check-up examinations are based on the clinical routine and the volunteer does not have to spend extra time due to the study. Therefore, it is not necessary to propose an additional insurance.

Data protection

The provisions of the data protection laws (in particular DSG MV and EU-DSGVO) are observed. All test materials and data are adequately pseudo-anonymized in accordance with the privacy policy. An assignment of the personal data to the study data may only be carried out by employees of the dental surgery of Dr. med. dent. [name] in Steina.

Statistical analysis plan

Number of cases

The total number of cases in the study was 60 people. 30 patients are assigned to the muscle training group and 30 patients are included in the comparison group with an equilibration splint.

In addition, the study groups are differentiated according to the categorical factor of gender.

Statistical analysis

The evaluation of the target variables is carried out using descriptive and inductive statistics.

In the descriptive statistical representation, the usual characteristic values such as frequency, mean values, standard deviation and range of values (minima, maxima) are used.

Possible differences in the study groups are analyzed using parametric (double t-test) and non-parametric (Mann-Whitney U-test) methods. The Chi²- test is used to analyze possible relationships between the nominally scaled values (e.g. gender). The interpretation is based on a 95% confidence interval. The hypothesis testing procedure is based on an error probability of 5% [p = 0.05], which is often used in studies.

The evaluation of the blinded data is carried out by [name].

Data management

Data collection

The data for each patient are taken from the electronic patient file of Dr. med. dent. [name] in Steina. This includes the questionnaire consisting of the baseline exmaination, x-rays, functional status, as well as the primary (pain when opening or closing the mouth) and secondary (occurrence of the cracking phenomenon when opening or closing the mouth, Janda degrees of strength in laterostrusion movement, interincisal opening distance) target variables.

The forms are filled out, dated and signed by the test subjects or persons who are authorized to document them (dental practice employees).

Data processing

The data entry in the electronic patient file is carried out by the examiner Dr.med.dent. [name] or his employees. All questionnaires and findings sheets that have been filled out by hand are scanned and also saved in the electronic file of each volunteer.

The use of the data takes place in accordance with legal regulations and requires a voluntarily submitted and signed declaration of consent by the test persons before participating in the clinical study.

The collected data may be passed on to [name] and the study director in pseudo-anonymized form for the purpose of scientific evaluation.

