The patient fills in a symptom-related questionnaire before the initial examination starts. The questionnaire is based on the current requirements of the DC / TMD. Demographic data as well as questions about general pain, headaches, jaw noises or locking are answered. In addition, each patient completes a questionnaire on the grading of chronic pain (Version 2.0), the Jaw Functional Limitation Scale (JFLS-8) and the Oral Behavior Checklist.

A functional examination is created during the baseline check-up. It is used to capture masticatory muscle and temporomandibular joint complaints based on a detailed anamnesis and subsequent clinical examination via palpation and inspection of the orofacial area. A standardized examination procedure adapted to the DC / TMD is used for this procedure.

During the screening examinations (after 2, 4 and 6 months), the functional status as well as the primary (pain when opening or closing the mouth) and secondary (occurrence of the cracking phenomenon when opening or closing the mouth, Janda degrees of strength for laterotrusion movement, interincisal opening) target variables will be collected.

Patient characteristics

Treatment groups

Treatment group 1: patients with anterior disc displacement with reduction **Therapy:** Static stretching and isometric contraction exercises of the lateral pterygoid muscle are used to strengthen and restore a physiological lateral movement of the mandible. The training is supervised in the dental practice and continued with selfexercises at home. The therapy is accompanied by an exercise movie on DVD produced by Dr.med.dent [name].

Treatment group 2: patients with anterior disc displacement with reduction. **Therapy:** Stabilization appliance for the lower jaw

Group size: 30 patients per group (60 patients in total)

Description of the recruitment: The patients will be recruited in the dental practice

Inclusion Criteria

- Orofacial pain in the joint or muscles, degree NRS≥3
- Clicking phenomenon during TMJ opening or closing movement
- Deviation movement during opening of the lower jaw
- Age: \geq 18 years
- Legal competence and presence of the signed declaration of consent

Exclusion Criteria

- Age <18 years
- Drug abuse
- Depression
- Polyarthritis

Test procedure

Examiners

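### Only the appliance arm has a dated 1-week visit and neither arm has a set adverse-event question, so early transient exercise effects may be under-recorded

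*Combined protocol and SAP*

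**What the plan says.** The appliance arm has its own early visit, headed "Control appointment for stabilization appliance group (1 week after integration"). Its described content is technical: "The surface contacts in the side teeth area as well as the incisor and canine guidance are checked again". The next heading, "First control appointment (2 months after start of therapy"), is the first dated control that applies to both arms. Further controls follow at 4 and 6 months.

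The section on risks of the treatment execution says that during muscle training "the volunteers may occasionally experience an increase in pain (similar to muscle soreness) and headache or dizziness may occur". It continues: "However, these side effects should disappear after the first week and regular exercising". It then adds: "In addition, the untrained muscles can be overloaded in the beginning".

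The exercise arm has two other kinds of contact. Under Treatment groups, "The training is supervised in the dental practice and continued with selfexercises at home", with no number or dates of sessions. Under Baseline examination, patients with coordination grade II or III are checked weekly until they reach grade I, and only then are they instructed in muscle training.

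Under Patient Safety the collection rule is "Adverse events are recorded and the connection (certain, likely, unlikely) assessed". Serious or unexpected effects go on a separate form. No question, visit or recall period is given for other events.

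**The concern.** The plan names one risk period for the experimental treatment, its start, and dates no contact in that period for the arm concerned. The comparator arm is seen by the dentist at 1 week. Where adverse events are noted without a set question, the number and timing of contacts tend to decide what is written down. Here the early contact differs by arm.

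Three things are at stake. First, a table of adverse events by arm, or a sentence on which treatment is better tolerated, could look better for exercise simply because there was less opportunity to record. Second, the protocol's expectation that these effects pass after the first week could not be checked from the data. Third, the pain scores do not fill the gap: the numeric rating scale is taken at baseline and at 2, 4 and 6 months, so a rise in pain in week 1 that then settles would not appear there either. The practitioner is also the examiner and is unblinded, which makes a standard way of asking more useful.

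**Working it through.** The plan gives no adverse-event rate and no recording probability, so there is no figure to reproduce. The check sets the sections side by side.

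**1. Dated contacts after treatment starts**

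| Time | Appliance arm | Exercise arm |
|---|---|---|
| 1 week | Control appointment (contacts and guidance) | None dated |
| 2 months | First control | First control |
| 4 months | Second control | Second control |
| 6 months | Third control | Third control |

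**2. Do the other exercise contacts cover the first week of training?**

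- The weekly coordination checks come before instruction in muscle training and apply only to grades II and III. They cannot observe effects of that training.
- The practice-based supervision has no dates. The Muscle Training section describes a demonstration at the practice and a film for self-instruction at home. A session in week 1 is possible, but the plan does not schedule one.

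**3. Length of the interval without a dated contact**

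Two months is about 61 days. From the end of week 1 to the first common control is 61 − 7 = 54 days, or 54 / 7 = 7.7 weeks. This applies to a patient whose therapy starts directly with muscle training. For patients who begin with coordination exercises, the plan does not say which day counts as the start.

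**4. Direction and size of any bias**

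Let p be a true rate of early transient events, equal in both arms for the purpose of the argument. Let c_E and c_A be the probabilities that such an event is recorded in the exercise and appliance arms. Then

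expected recorded difference (exercise minus appliance) = p × c_E − p × c_A = p × (c_E − c_A).

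This is negative, so exercise looks safer, whenever c_E is below c_A. It is zero when the two are equal. The visit schedule makes c_E below c_A plausible. The documents give none of the three quantities, so no value can be put on the difference.

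**5. Is a planned analysis affected?**

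The Target criteria section lists pain, clicking, Janda force and interincisal opening. The Statistical analysis section evaluates the target variables. Adverse events are not among them, and the Data collection section does not name them among the items taken from the patient file. No planned primary or secondary analysis uses the affected data.

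**The case against.** The case on the other side is substantial. Adverse events are not an outcome and the SAP plans no comparison of them. The collection rule is not tied to visits, so an event could be noted whenever a patient reports it. Supervised training might well include a session in week 1. The appliance visit is described as a check of fit, with no adverse-event question, so more contact has been shown but more recording has not. Appliance effects that arise after week 1 also wait until 2 months. Exercise effects that persist would still be visible then.

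Most of this stands, and it limits the claim. A reader might infer that exercise harms are first seen at 2 months and only by recall. The documents do not say so: undated supervision is not the same as no contact. A reader might also infer that the trial's safety comparison favours exercise. There is no such comparison in the plan, and unequal recording is a risk, not an established fact. Nor can percentages be attached without inventing an event rate and a recording probability for each arm.

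What the objection does not remove is the schedule itself. A dated early contact exists in one arm only, while the protocol expects early effects in the other. A tabulation by arm is also foreseeable, because events are recorded with a causality rating in a two-arm trial and the risk section already passes an overall judgement on the risks of both treatments.

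**Conclusion.** The point holds in a limited form. Scheduled early contact differs by arm, the way adverse events are elicited is unspecified in both, and the exercise arm has no dated contact from instruction in muscle training to 2 months. Early transient exercise effects may be under-recorded, and any adverse-event table by arm or tolerability statement could be biased towards exercise.

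The size is unknown. The direction rests on two assumptions: that seeing the dentist at 1 week gives appliance patients some added chance of having an event noted, and that undated supervision does not give exercise patients the same chance. If either fails, the bias shrinks towards zero. The efficacy analyses are untouched. The change is worth making because it is cheap and can only be made before the data are collected.

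**What to change.** Change data collection only; nothing in either treatment needs to alter.

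- Write one adverse-event question, worded identically for both arms, with onset date, end date and the existing causality rating.
- Ask it 1 week after the start of therapy and at 2, 4 and 6 months. In the appliance arm, use the existing 1-week visit. In the exercise arm, use a short call or message from practice staff.
- State from which day the week is counted for patients who do coordination exercises first. The early effects that the risk section describes belong to muscle training.
- Add a line to the SAP on how adverse events will be summarised by arm.

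If no 1-week contact is added for the exercise arm, base any table by arm on events elicited by the common question at 2, 4 and 6 months, and list events found only at the 1-week appliance visit separately.

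The cost is about 30 short contacts, one for each exercise patient, plus one form question at visits that already exist. The Insurance section says that the study takes no additional time from participants, and this needs a small edit. The fallback needs only the question and the reporting rule.
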